7.1.2 Randomization and Stratification

N/A

7.1.3 Populations for Analysis

All patients enrolled will be included in the safety analysis.

7.1.4 Procedures for Handling Missing, Unused, and Spurious Data

All available data will be included in the data listings and tabulations. Where appropriate, imputations of values for missing data will be performed using last observation carried forward and specified in the Statistical Analysis Plan. All data recorded on the CRF will be included in the data listings that will accompany the clinical study report.

7.1.5 Demographic and Baseline Characteristics

Demographic and baseline characteristics in all enrolled patients will be reported in a table format. These will include age, gender, race, ethnicity, cause of ESRD, history of sensitization (transfusion, previous transplantation, pregnancy), type of renal replacement therapy, baseline cPRA, CBC, LFTs, and medications.

7.1.6 Efficacy Analysis

Primary outcome will be a decline in cPRA > 20%. Secondary outcome will be kidney transplantation within 12 months of therapy. These outcomes will be assessed using paired t-Test, Kaplan-Meier methods and log rank tests, where appropriate. In addition, we will analyze the change in HLA antibody strength by comparing the MFI values pre and post therapy.

7.1.7 Pharmacokinetics/Pharmacodynamics/Biomarkers (if applicable)

N/A

7.1.8 Safety Analysis

Together with the UW ICTR Data Monitoring Committee (DMC) we will develop a detailed a data and safety monitoring plan (DSMP) which will ensure ongoing safety of participating patients commensurate with the level of risk and complexity of the protocol treatment to minimize risks, integrity of trial data and scientific validity of the trial. The development of the DSMP will be guided by the NIH Policy for Data and Safety Monitoring and by the FDA Guidance on the Establishment and Operation of Clinical Trial Data Monitoring Committees. The plan will make certain that review of the conduct of research is rigorous, independent and objective, interim safety and efficacy data is collected and presented and progress towards achieving study goals is made. It will cover policies and procedures for reporting adverse events to the DSMB, IRB, and the FDA.

The safety analysis will focus on infections, malignancies, hematological complications including leucopenia, anemia, and thrombocytopenia, cardiovascular complications and events, distal neuropathy, gastrointestinal symptoms, and immunosuppression-related adverse effects. Patients will have a physical exam 5 times (beginning and end of the study, and quarterly during the study) following enrollment: Days 1, 85, 169, 253, and 373 (+ 6, - 3 for all visits except for visit 1).

- Day 1: Prior to treatment initiation. H&P, Labs, Bone Marrow Aspirate
- Day 85 + 6, - 3: Prior to treatment dose. H&P, Labs
- Day 169 + 6, - 3 Prior to treatment dose. H&P, Labs
- Day 253 + 6, - 3 Prior to treatment dose. H&P, Labs
- Day 373 + 6, - 3 After treatment completion, H&P, Labs, Bone Marrow Aspirate
- At each of these visits, the patients will undergo a medical history and physical exam, reviewing the adverse event data, vital signs, monthly labs, changes in patients' health status and medications.
- Study drug will be dispensed at each month's in-person visit, prior the initiation of the next cycle, and after reviewing the AEs and monthly labs.

Liver Function Tests (LFTs) will be conducted twice a month for the first 3 months, then monthly thereafter. The Complete Blood Count (CBC) will be checked monthly.

7.1.9 Interim Analysis

We will utilize the UW ICTR Data Monitoring Committee (DMC) to oversee the study and is described further in section 9.1 Source documents may be reviewed to allow the DMC to independently judge whether the overall integrity and conduct of the protocol remain acceptable based on data provided and reported by the Principal Investigator. The DMC will make recommendations to the Principal investigator that could include actions of continuation, modification, suspension or termination.

7.1.10 Study Stopping Rules

Subject Stopping Rules

Patients will be informed that they have the right to withdraw from the study at any time for any reason, without prejudice to their medical care. The investigator also has the right to withdraw patients from the study for any of the following reasons:

- If study drug is discontinued due to AE

If a subject is withdrawn due to an adverse event, the dose adjustment, modification and withdrawal procedures related to adverse events described in section 6.3 of the clinical protocol will be followed.

- Protocol violation
- Lost to follow-up
- Study terminated
- Non-compliance

Study Stopping Rules

Serious Adverse Events (SAEs) as described below, will be reviewed to determine if additional risk could be posed to the subject in question or others participating in the study. If it is determined that a serious adverse event, new information, or an unanticipated event could pose a potential risk to subjects, the DMC and/or the investigator may decide to stop the study.

8. ADVERSE EVENTS

Adverse drug reactions such as thrombocytopenia, diarrhea, fatigue, nausea, vomiting, and rash have been associated with ixazomib treatment.

8.1 Definitions

8.1.1 Adverse Event Definition

Adverse event (AE) means any untoward medical occurrence in a patient or subject administered a pharmaceutical product; the untoward medical occurrence does not necessarily have a causal relationship with this treatment. An AE can therefore be any unfavorable and unintended sign (including an abnormal laboratory finding), symptom, or disease temporally associated with the use of a medicinal (investigational) product whether or not it is related to the medicinal product. This includes any newly occurring event, or a previous condition that has increased in severity or frequency since the administration of study drug. AEs will be assessed at study visits and during the final follow-up study visit. In addition, data on rejection, graft, and patient survival will be collected for 6 months following kidney transplantation.

An abnormal laboratory value will not be assessed as an AE unless that value leads to discontinuation or delay in treatment, dose modification, therapeutic intervention, or is considered by the investigator to be a clinically significant change from baseline. These AEs will be entered into the OnCore system.

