1 Bone Marrow Aspiration must be done before drug administration and at one of the following endpoints: one month (+6, -3 days) after the end of the 12 month study, cPRA decline > 20%, time of transplant, or time of subject withdrawal from the study.

Table 2-1 (b)-Schedule of events (last six cycles)

| Procedures Performed | Cycle 7 | | | Cycle 8 | | | Cycle 9 | | | Cycle 10 | | | Cycle 11 | | | Cycle 12 | | | Final visit 1M after last dose | ETV or Unscheduled Visit |
|------------------------------------|---------|-----|-----|---------|-----|-----|---------|-----|-----|----------|-----|-----|----------|-----|-----|----------|-----|----------------|--------------------------------|--------------------------|
| Treatment Days | 169 | 176 | 183 | 197 | 204 | 211 | 225 | 232 | 239 | 253 | 260 | 267 | 281 | 288 | 295 | 309 | 316 | 323 | 373 | |
| Ixazomib and dexamethasone | X | X | X | X | X | X | X | X | X | X | X | X | X | X | X | X | X | X | | |
| Medical History | X | | | | | | | | | X | | | | | | | | | X | |
| Physical Exam | X | | | | | | | | | X | | | | | | | | | X | |
| Vital Signs (T, P, R, BP) | X | | | X | | | X | | | X | | | X | | | X | | X | X | |
| AE Assessment | X | | | X | | | X | | | X | | | X | | | X | | X | X | |
| Electrocardiogram (ECG) | X | | | | | | | | | | | | | | | | | | X | |
| Echocardiogram | X | | | | | | | | | | | | | | | | | | X | |
| Medication History | X | | | X | | | X | | | X | | | X | | | X | | X | X | |
| Drug Accountability | | | | X | | | X | | | X | | | X | | | X | | X | X | |
| Pregnancy Test (where appropriate) | | | | | | | | | | | | | | | | | | | | |
| CBC | X | | | X | | | X | | | X | | | X | | | X | | | X | |
| LFTs | X | | | X | | | X | | | X | | | X | | | X | | | X | |
| cPRA | X | | | | | | | | | X | | | | | | | | | X | |
| BAFF/APRIL | X | | | | | | | | | X | | | | | | | | | X | |
| DSA Antibodies | X | | | | | | | | | X | | | | | | | | | X | |
| Bone Marrow Aspiration | | | | | | | | | | | | | | | | | | X ¹ | X ¹ | |

TABLE OF CONTENTS

| | |
|---|----|
| PROTOCOL SUMMARY..... | 3 |
| STUDY OVERVIEW DIAGRAM (optional)..... | 6 |
| SCHEDULE OF EVENTS..... | 7 |
| LIST OF TABLES AND FIGURES (OPTIONAL)..... | 11 |
| LIST OF ABBREVIATIONS AND GLOSSARY OF TERMS..... | 12 |
| 1. BACKGROUND AND STUDY RATIONALE | 13 |
| 1.1 Scientific Background | 13 |
| 1.1.1 Disease Under Treatment..... | 13 |
| 1.1.2 Ixazomib (MLN9708) | 14 |
| 1.2 Preclinical Experience | 14 |

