1.10 Potential Risks and Benefits

Please refer to the current ixazomib IB and SMA for a complete list of the risks of ixazomib. The clinical benefit of ixazomib continues to be studied in a comprehensive and global development plan that involves studies sponsored by Millennium. Ixazomib appears to show a significant impact on the production of allo antibodies in preclinical studies of AMR. The preliminary findings are favorable when considering historical and currently available therapies for the patient populations evaluated. Though additional data are needed to characterize the clinical benefit of this drug, the emerging data supports expanded development of ixazomib for the treatment of patients with advanced malignancy.

This study will be conducted in compliance with the protocol, good clinical practice (GCP), applicable regulatory requirements, and International Conference on Harmonisation (ICH) guidelines.

Compliance with eligibility criteria: The PI will sign-off on the eligibility checklist for each subject prior to study drug dispensation.

The risks to subjects in this trial will be minimized by compliance with eligibility criteria, clinical monitoring, adherence to protocol contraception requirements and investigator guidance regarding specific safety areas.

The specific safety areas that will be closely monitored in this subject population are;

Ixazomib: thrombocytopenia, diarrhea, fatigue, nausea, vomiting, rash, risk of reactivation of herpes infection, neutropenia, fluid deficit, hypotension, posterior reversible encephalopathy syndrome (PRES), and transverse myelitis.

Bone Marrow Aspiration Risks: This procedure may be very painful; however, the pain only lasts for about 15 to 30 seconds. The hip area may be sore for a day or two. It is possible, but not likely that the subject could get an infection or have a large amount of bleeding. In very rare cases, people might have an allergic reaction to the local anesthesia. The allergic reaction could include rash/hives, flushing of the face, itching, wheezing and tightness in the throat.

For subjects that are on warfarin, INR levels will be checked prior to the BMA, and pressure will be applied for

- 10 minutes after the procedure if INR 1.5-2
- 15 minutes after the procedure if INR 2-2.5
- 20 minutes after the procedure if INR > 2.5

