4.3 Duration of Study

Participants will be followed for the entire length of treatment, plus one month. All subjects, including those that receive a kidney transplant and those that do not, will continue to be monitored for one month following the last dose of study drug to monitor for and address potential adverse events from treatment (Final visit on day 373 + 6, - 3). Thereafter, dialysis nephrologists will routinely follow the patients. For those transplanted, data on acute rejection, graft and patient survival will be collected for 6 months after surgery.

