Duration of Treatment and Follow-up. All participants, those that receive a kidney transplant during the defined period and those that do not will be followed for the entire length of treatment, plus one month following the last dose of the study drug. All subjects will be asked to return for a final study visit approximately one month following the last dose of study drug. During this final study visit, subjects will undergo physical examination, bone marrow aspirate collection, CBC, LFT check, ECG and echocardiogram.

Bone Marrow Aspirate Collection Procedure: Subjects will be given the option of having the bone marrow aspirate performed under conscious sedation or local anesthetic only. The bone marrow aspirate will be collected in a transplant clinic room. If the bone marrow aspiration is done under conscious sedation, subjects will be given instructions to fast for six hours before the procedure (medications are allowed) and not to drive themselves home or operate dangerous equipment after the procedure.

Measurement of effect. We will determine the effect of ixazomib by measuring cPRA, whether patients receive a kidney transplant while participating in the study, antibody strength by MFI, and the toxicity (measured by the incidence of adverse events) of the treatment quarterly up to the end of the study.

Ixazomib Administration

All protocol-specific criteria for administration of study drug must be met and documented before drug administration. Study drug will be dispensed only to eligible patients by a member of the study team. Patients should be monitored for toxicity, as necessary, and doses of ixazomib should be modified as needed to accommodate patient tolerance to treatment; this may include symptomatic treatment, dose interruptions, and adjustments of ixazomib dose (see Section 6.3).

Capsules of ixazomib will also be referred to as study drug. Study drug will be supplied by Millennium as capsules 0.5, 2.3, and 3.0 mg ixazomib. The prescribed administration of ixazomib doses in this study is 9 mg ixazomib in a 28 day cycle. Patients should be instructed to swallow ixazomib capsules whole, with water, and not to break, chew, or open the capsules. Ixazomib should be taken on an empty stomach (no food or drink) at least 1 hour before or at least 2 hours after food. Each capsule should be swallowed separately with a sip of water. A total of approximately 8 ounces (240 mL) of water should be taken with the capsules.

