8.2 Procedures for Reporting Serious Adverse Events

AEs may be spontaneously reported by the patient and/or in response to an open question from study personnel or revealed by observation, physical examination, or other diagnostic procedures. When possible, signs and symptoms indicating a common underlying pathology should be noted as one comprehensive event. For serious AEs, the investigator must determine both the intensity of the event and the relationship of the event to study drug administration.

AEs which are serious must be reported to Millennium Pharmacovigilance (or designee) from the first dose of study drug through 30 days after administration of the last dose of ixazomib. Any SAE that occurs at any time after completion of ixazomib treatment or after the designated follow-up period that the sponsor-investigator and/or sub-investigator considers to be related to any study drug must be reported to Millennium Pharmacovigilance (or designee). In addition, new primary malignancies that occur during the follow-up periods must be reported, regardless of causality to study regimen, up to one month after the last dose of the investigational product, starting from the first dose of study drug. All new cases of primary malignancy must be reported to Millennium Pharmacovigilance (or designee).

Planned hospital admissions or surgical procedures for an illness or disease that existed before the patient was enrolled in the trial are not to be considered AEs unless the condition deteriorated in an unexpected manner during the trial (e.g., surgery was performed earlier or later than planned). All SAEs should be monitored until they are resolved or are clearly determined to be due to a patient's stable or chronic condition or intercurrent illness(es).

Since this is an investigator-initiated study, the principal investigator [name], also referred to as the sponsor-investigator, is responsible for reporting serious adverse events (SAEs) to any regulatory agency and to the sponsor- investigator's EC or IRB.

Regardless of expectedness or causality, all SAEs (including serious pretreatment events) must also be reported in English to Millennium Pharmacovigilance (or designee):

Fatal and Life Threatening SAEs within 24 hours of the sponsor-investigator's observation or awareness of the event

All other serious (non-fatal/non life threatening) events within 4 calendar days of the sponsor-investigator's observation or awareness of the event

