9. SAFETY MONITORING

9.1 Safety Monitoring

The investigator is responsible for monitoring the safety of subjects who have enrolled in the study. For this study, adverse events will be solicited from subjects to identify an occurrence or worsening of an unintended sign or symptom, related to the ingestion of the study drug. The study team will ask subjects prior to each cycle if they experienced any new medical related signs or symptoms since taking the study drug. Subjects will be asked about any adverse events they may have experienced again monthly, prior to each cycle, and at the five study visits. Only the adverse events considered related (possibly, probably or definitely) to the ingestion of the study drug will be entered into and managed in the ICTR OnCore system quarterly.

At each visit, subjects will be assessed for AEs by the study team. They will be examined by the principal investigator 5 times (please see tables 2-1 a-b and Figure 1, below): Days 1, 85, 169, 253, and 373 + 6, - 3).

- Day 1: Prior to treatment initiation. H&P, Labs, Bone Marrow Aspirate
- Day 85 + 6, - 3: Prior to treatment dose. H&P, Labs
- Day 169 + 6, - 3 Prior to treatment dose. H&P, Labs
- Day 253 + 6, - 3 Prior to treatment dose. H&P, Labs
- Day 373 + 6, - 3 After treatment completion, H&P, Labs, Bone Marrow Aspirate
- Study drug will be dispensed at each month's in-person visit, prior the initiation of the next cycle, and after reviewing the AEs and monthly labs.

- Patients will undergo monthly CBC and bi-weekly liver function tests (LFTs) for the first three months. After the first 3 months, CBCs and LFTs will be done monthly. cPRA, BAFF/APRIL, DSA and antibodies will be checked every three months (5 times total). Bone marrow aspirates will be collected at the beginning and at one of the following time points: one month (+ 6, - 3 days) after the end of the 12 month study, cPRA<80%, time of transplant, or time of subject withdrawal from the study.
- Additional visits may be required if the subject has to hold treatment and needs to return to the clinic for blood draws to confirm eligibility to continue. Please see Table 4-3, Dose Adjustments for Hematologic Toxicities for dose adjustment plan.

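### A second marrow taken at the Day 373 visit coincides with the last scheduled adverse event assessment, so delayed bleeding or infection from it is not actively sought

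*Combined protocol and SAP*

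**What the plan says.** **Timing of safety questions.** Section 8.1.1: "AEs will be assessed at study visits and during the final follow-up study visit". Table 2-1(b) marks AE assessment at the Day 373 visit and at no later scheduled point. Section 4.3 then says: "Thereafter, dialysis nephrologists will routinely follow the patients". The only later study data are rejection, graft and patient survival for six months in transplanted subjects.

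**Timing of the second marrow.** Section 6.2: "During this final study visit, subjects will undergo physical examination, bone marrow aspirate collection", among other tests. Section 4.1 also lists the marrow at Day 373. Section 4.1 and the schedule footnote allow it at one of four points: a month after the study ends, on a cPRA decline of more than 20%, at transplant, or at withdrawal.

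**Reporting.** Section 8.2 requires SAEs to go to the drug supplier "from the first dose of study drug through 30 days after administration of the last dose of ixazomib". Later SAEs go to the supplier only if judged related to a study drug, apart from a separate rule for new malignancies. The causality item on the SAE report concerns study drug only. Section 9.1 ties solicitation to taking ixazomib ("adverse events will be solicited from subjects to identify an occurrence or worsening of an unintended sign or symptom, related to the ingestion of the", where the sentence goes on to name the drug), and limits OnCore entry to AEs considered at least possibly drug-related. The end of Section 9.1 says instead that all AEs and SAEs are entered. Section 9.1 also sends reportable events from study procedures to the IRB, with no end date.

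**Known risk.** Section 1.10 says of the aspiration: "It is possible, but not likely that the subject could get an infection or have a large amount of bleeding".

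**The concern.** A haematoma or site infection from an aspiration may appear hours or days after the needle is withdrawn. If the procedure and the final safety question fall at the same visit, the question comes too early to find these events. The aspiration serves the mechanistic aim, so subjects carry its risk for research purposes, and Section 1.10 expects that some will be on warfarin with the dose left unchanged. Infections are also a named category of the safety endpoint in Section 3.1. A report of no late complications after such an aspiration would be hard to interpret, because nobody was scheduled to ask. Wording that ties solicitation, causality and one of the two database rules to study drug adds to the difficulty: a purely procedural event has no clear place to be recorded.

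**Working it through.** **Inputs.** Twelve 28-day cycles with dosing on days 1, 8 and 15 (Section 6.2). The last columns of Table 2-1(b) read "309 | 316 | 323 | 373", the final one headed "Final visit 1M after last dose". The visit window is +6/-3 days (Section 4.1). The supplier SAE window is 30 days after the last dose (Section 8.2). There are 10 subjects (Section 4.2), each with two planned aspirations.

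**1. Last dose.** 11 × 28 + 15 = Day 323, which agrees with the table.

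**2. Final visit against its label.** 373 - 323 = 50 days, not one month. Taking a month as 28, 30 or 31 days:
- from the last dose: Day 351, 353 or 354;
- from the end of cycle 12 (12 × 28 = Day 336): Day 364, 366 or 367;
- from Day 365: Day 393, 395 or 396.

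None lies in the permitted range, Day 370 to 379. The label is not reproduced.

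**3. Distance from the supplier window.** The window closes on Day 323 + 30 = 353.
- Nominal gap: 373 - 353 = 20 days.
- With the visit window: 370 - 353 = 17 to 379 - 353 = 26 days.
- If the last dose also moves within +6/-3: 370 - (329 + 30) = 11 to 379 - (320 + 30) = 29 days.
- If dosing runs d days late and the visit stays at Day 373: 20 - d days.

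**4. Does the problem depend on the gap?** No. A visit at Day 353 makes the gap 353 - 353 = 0, but the marrow would then be taken on the last day of the window, again with no scheduled contact afterwards.

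**5. Who is affected.** 10 × 2 = 20 aspirations, of which at most 10 are second ones. A marrow prompted by a cPRA decline at Day 85, 169 or 253 leaves 288, 204 or 120 days to Day 373, with the next monthly AE visit 28 days later if treatment continues. Table 2-1(b) also shows a marrow mark in the Day 323 column; a subject sampled then would be asked about AEs 50 days later. Section 9.1 words the cPRA trigger differently from Section 4.1 (a cPRA below 80%), so the documents do not settle who is sampled early.

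**6. Early leavers.** The early termination visit, which includes a marrow, is within 7 days of discontinuation (Section 4.1). It falls inside the 30-day window if discontinuation is within 30 - 7 = 23 days of the last dose. Sections 4.3 and 6.2 also ask all subjects to return about a month after the last dose.

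**7. Routes open to a procedural event that appears after Day 373.**
- Scheduled AE question: none.
- Supplier SAE report: not required unless attributed to study drug.
- OnCore: excluded by one rule in Section 9.1, included by the other.
- IRB: open without a time limit if reportable, but dependent on the team learning of the event.

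**The case against.** The strongest reply is that the plan does not shut these events out. Section 9.1 has an untimed duty to report procedure-related events to the IRB, and sends reportable events, SAEs among them, to the IRB and the DMC. The 30-day limit in Section 8.2 governs reports to the supplier; it does not end the study's own reporting. Section 8.2 accepts spontaneous reports, Section 9.1 has staff ask about any new signs or symptoms, and an immediate reaction can be recorded at Day 373. All of this stands. A reader might infer that late complications can never be known, or that SAE reporting is over by Day 353; the documents support neither. What remains is that every route open after Day 373 is passive.

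A reader might also infer that all ten second marrows are unfollowed and that early leavers are in the same position. The alternative triggers and the return visit in Sections 4.3 and 6.2 count against both, although the plan does not say clearly how the early termination visit and that return visit relate.

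The risk should not be inflated. Section 1.10 requires an INR check before aspiration in subjects on warfarin and graded pressure afterwards. Day 373 is 50 / 9.5 = 5.3 of the half-lives quoted in Section 1.4 after the last dose, and a blood count is scheduled that day, so drug-related thrombocytopenia is a weak argument for completers. A late marrow complication would not alter the primary efficacy result, nor the safety test in Section 7.1, which counts discontinuations due to AEs. The 20 days also comes partly from the mislabelled visit day, though step 4 shows that correcting the day would not close the gap in ascertainment.

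**Conclusion.** The point holds in a limited form. For a subject who reaches the final visit without an earlier marrow trigger, the procedure and the last scheduled AE assessment coincide, and delayed bleeding or infection is not actively ascertained. This concerns at most 10 of 20 planned aspirations; the true number depends on cPRA decline, transplant and withdrawal and cannot be fixed in advance. The 20-day distance from the close of the supplier window assumes undelayed dosing and a visit on Day 373 as written. The absence of a later contact does not depend on that distance. Early leavers are a secondary case. This is a gap in safety ascertainment that is cheap to close, not a threat to the primary analyses.

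**What to change.** In Sections 8.1.1 and 8.2, add wording to this effect: 'Within a few days of every bone marrow aspiration, study staff telephone the subject and ask about bleeding, infection and pain. AE and SAE collection continues through that contact, even if it falls more than 30 days after the last dose. Relation to study procedure is recorded separately from relation to study drug.' Aspiration events can then be reported in their own table.

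Two inconsistencies should be reconciled in the same amendment: Day 373 against its one-month label (Table 2-1(b), Sections 4.1, 4.3 and 6.2), and the two statements in Section 9.1 on which AEs enter OnCore.

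The cost is protocol wording, one extra field on the AE form and at most about 20 short calls (10 subjects × 2 aspirations) by existing staff. No visit or test is added.
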